4. STUDY DESIGN

4.1. Overall Design

This Phase 1/2 study will evaluate the safety, efficacy, PK, and PD of itacitinib in participants with post-lung transplant BOS.

Phase 1 is a dose selection run-in that will employ a randomized, open-label, parallel-cohort design to assess the safety, tolerability, PK, and PD and to determine the RP2D of itacitinib in participants with post-lung transplant BOS. A total of 24 participants with Grade 1, 2, or 3 BOS will be assigned to receive 1 of 3 itacitinib dose levels ($n = 8$ each); see [Table 9](#) for additional details regarding itacitinib dose levels. Each Phase 1 dose level will enroll a maximum of 2 participants with Grade 3 BOS. Participants will be randomized to 1 of 3 dose levels using an IRT system. Upon completion of Phase 1 enrollment, the RP2D will be selected on the basis of AE, laboratory, PK, and PD observations through the Week 12 visit. Additionally, an efficacy analysis will be performed to determine the FEV_1 response rate for all participants treated for ≥ 12 weeks. The study will proceed to Phase 2 if ≥ 1 responses (defined as $\geq 10\%$ absolute increase in FEV_1 compared to baseline, confirmed by 2 consecutive spirometric assessments ≥ 1 week apart) are observed at the dose level selected as the RP2D.

Phase 2 will employ a single-arm, open-label design to evaluate the efficacy and further characterize the safety of itacitinib at the RP2D.

Itacitinib treatment in Phase 1 and Phase 2 will continue until progression of BOS (defined as a $\geq 10\%$ absolute decrease from baseline in FEV_1 , confirmed by 2 consecutive spirometric assessments ≥ 3 weeks apart), unacceptable toxicity, loss of clinical benefit, or withdrawal of consent. Additional criteria for treatment discontinuation are detailed in Section [7.1](#).

4.2. Overall Study Duration

The study begins when the first participant signs the ICF. The end of the study may be designated as the timepoint at which all participants have discontinued the study or a minimum of 6 months after initial study treatment administration, at which time a database lock of the study may occur to allow for analysis of the study data. Any participant continuing on treatment at the time of database lock will continue to be treated and followed per Protocol. The additional treatment and follow-up data will be reported in an addendum to the CSR.

4.3. Study Termination

The investigator retains the right to terminate study participation at any time, according to the terms specified in the study contract. The investigator is to notify the IRB/IEC in writing of the study's completion or early termination, send a copy of the notification to the sponsor or sponsor's designee, and retain 1 copy for the site study regulatory file.

The sponsor may terminate the study electively or if required by regulatory decision. If the study is terminated prematurely, the sponsor will notify the investigators, the IRBs and IECs, and regulatory bodies of the decision and reason for termination of the study.

5. STUDY POPULATION

Deviations from eligibility criteria are not allowed because they can potentially jeopardize the scientific integrity of the study, regulatory acceptability, and/or participant safety. Therefore, adherence to the criteria as specified in the Protocol is essential. Prospective approval of Protocol deviations to recruitment and enrollment criteria, also known as Protocol waivers or exemptions, are not permitted.

5.1. Inclusion Criteria

Participants are eligible to be included in the study only if all of the following criteria apply:

1. Male or female, 18 years of age or older.
2. Ability to comprehend and willingness to sign a written informed consent and assent (when appropriate) according to institutional standards and willingness to comply with all study visits and procedures.
3. Double lung transplantation \geq 1 year before informed consent.
4. Documented post-transplant baseline FEV₁ (average of the 2 highest values measured \geq 3 weeks apart per ISHLT criteria [[Meyer et al 2014](#)]) following functional recovery and stabilization post-lung transplantation.
5. Confirmed BOS progression to Grade 1, 2, or 3 (per ISHLT 2002 criteria [[Estenne et al 2002](#)]) diagnosed within 1 year of screening.
 - a. Grade 1 BOS is defined as a fractional decrease in FEV₁ to 66-80% of post-transplant baseline FEV₁.
 - b. Grade 2 BOS is defined as a fractional decrease in FEV₁ to 51-65% of post-transplant baseline FEV₁.
 - c. Grade 3 BOS is defined as a fractional decrease in FEV₁ to \leq 50% of post-transplant baseline FEV₁.

OR

Confirmed BOS Grade 1, 2, or 3 diagnosed within 2 years of screening (based on the above definitions) AND:

- a. A \geq 200 mL decrease in FEV₁ in the previous 12 months OR
- b. A \geq 50 mL decrease in FEV₁ in the last 2 measurements.

Note: BOS grade must be determined by the average of 2 measurements made \geq 3 weeks apart.

6. Participants may be taking azithromycin and/or montelukast for BOS, however, treatment must have been initiated \geq 3 months before screening and must be at a stable dose.
7. If a participant is being treated with systemic corticosteroids for BOS, then the dose must be stable for \geq 4 weeks before screening.

Note: Participants who have recently undergone a steroid taper and who are currently taking physiologic doses (\leq 10 mg/day prednisone equivalent) are not required to have been on a stable dose for \geq 4 weeks before screening.

8. Willingness to avoid pregnancy or fathering children based on the criteria below.
 - a. Men must agree to take appropriate precautions to avoid fathering children (with at least 99% certainty) from screening through 90 days after the last dose of study drug and must refrain from donating sperm during this period. Permitted methods that are at least 99% effective in preventing pregnancy (see [Appendix A](#)) should be communicated to the participants and their understanding confirmed.
 - b. Women of childbearing potential must have a negative serum pregnancy test at screening and before the first dose on Day 1 and must agree to take appropriate precautions to avoid pregnancy (with at least 99% certainty) from screening through safety follow-up. Permitted methods that are at least 99% effective in preventing pregnancy (see [Appendix A](#)) should be communicated to the participants and their understanding confirmed.
 - c. Women of nonchildbearing potential (ie, surgically sterile with a hysterectomy and/or bilateral oophorectomy OR ≥ 12 months of amenorrhea) are eligible.
9. If a participant is being treated with a strong CYP3A inhibitor (see [Appendix C](#)), then the dose must be stable for > 4 weeks before the first dose of study drug.

5.2. Exclusion Criteria

Participants are excluded from the study if any of the following criteria apply:

1. History of a single lung transplant.
2. FEV₁ decline attributable to cause(s) other than BOS, including but not limited to clear evidence of RAS, inflammatory complications of the lung allograft, antibody mediated rejection, infection, airway dysfunction, allograft compression, impaired graft inflation, vascular obstruction, weight gain, or organizing pneumonia.
3. For participants with Grade 3 BOS as defined in inclusion criterion #5, FEV₁ at screening $< 35\%$ of post-transplant baseline.
4. Receipt of any other systemic treatment specifically for BOS (with the exception of azithromycin and montelukast), including extracorporeal photopheresis, alemtuzumab, and/or ATG within the timeframes outlined in Section [6.3.3](#) and Section [6.3.4](#) (as applicable).
5. Epstein-Barr virus-negative participants (at the time of transplant) who received donor EBV IgG positive lungs.
6. Participants who have received lungs from HCV-infected donors.
7. Removed during Protocol Amendment 2.
8. Participants who have had any significant change (eg, addition of new agents) in an immunosuppressive regimen in the 4 weeks before screening.

Note: Adjustments to dosage of maintenance immunosuppression (eg, tacrolimus) to maintain therapeutic levels are encouraged. Monitoring of CNI levels and any other agents that are used for maintenance immunosuppression (eg, mTORi) for which therapeutic drug monitoring is routinely performed as local standard of care is required at all study visits through Week 8.

9. Participant is hospitalized as an inpatient at the time of consent or at study Day 1.
Note: Participants who are not hospitalized at the time of informed consent but are later hospitalized during the screening period may be enrolled as long as all other eligibility criteria continue to be met.
10. Untreated and/or symptomatic GERD.
11. Significant infectious comorbidities including invasive fungal disease, B. Cepacia, non-TB mycobacteria, or TB.
12. History of diffuse alveolar hemorrhage.
13. Receipt of JAK inhibitor therapy after lung transplant for any indication. Treatment with a JAK inhibitor before lung transplant is permitted.
14. Participants with laboratory values at screening defined in [Table 7](#).

Table 7: Exclusionary Laboratory Values

Laboratory Parameter	Exclusion Criterion
a	ANC < $1.5 \times 10^9/L$
b	Platelet count < $120 \times 10^9/L$
c	Hemoglobin < 9.0 g/L
d	AST or ALT $\geq 2 \times ULN$
e	Bilirubin $\geq 1.5 \times ULN$, unless due to Gilbert's syndrome
g	Creatinine clearance < 30 mL/min
h	Albumin < 3 g/dL
i	INR $> 1.5 \times ULN$

15. Active HBV or HCV infection that requires treatment, or at risk for HBV reactivation (ie, positive HBsAg). Participants with negative HBsAg and positive total HBc antibody may be included if HBV DNA is undetectable at the time of screening. Participants who are positive for HCV antibody are eligible only if PCR is negative for HCV RNA. Participants whose immune status is unknown or uncertain must have results confirming immune status before enrollment.
16. Known HIV infection.
17. History of active malignancy within 3 years of screening, excluding superficial basal and squamous cell carcinoma of the skin, DCIS, low-risk prostate cancer (Gleason score of 6 and a prostate-specific antigen measurement of 10 ng/mL or less and a stage of T2a or less), and adequately treated carcinoma in situ of the cervix. Additional prior or active malignancies may be allowed with approval from the medical monitor.
18. Women who are pregnant or breastfeeding.
19. Anticipated need for live (including attenuated) vaccines during the first year of study.

20. Treatment with an investigational agent, procedure, or device within 30 days of enrollment, or within 5 half-lives of the investigational product, whichever is longer.
21. Known allergies, hypersensitivity, or intolerance to any of the study medications, excipients, or similar compounds.
22. Inability or unlikelihood of the participant to comply with the dose schedule and study evaluations, in the opinion of the investigator.
23. Any condition that would, in the investigator's judgment, interfere with full participation in the study, including administration of study drug/treatment and attending required study visits; pose a significant risk to the participant; or interfere with interpretation of study data.
24. Inability of the participant (or parent, guardian, or legally authorized representative) to comprehend the ICF or unwillingness to sign the ICF.

5.3. Lifestyle Considerations

5.3.1. Meals and Dietary Restrictions

Participants should be instructed to refrain from the consumption of pomegranates or pomegranate juice and grapefruit or grapefruit juice, as these are known to inhibit cytochrome CYP3A enzymes and may increase the exposure to itacitinib.

5.4. Screen Failures

Screen failures are defined as participants who consent to participate in the clinical study but are not subsequently randomly assigned to study treatment.

Participants who do not meet the criteria for enrollment into this study (screen failure) may be rescreened once if the investigator believes that there has been a change in eligibility status. Participants who rescreen must reconsent and be assigned a new participant number.

Tests with results that fail eligibility requirements may be repeated once during the screening period if the investigator believes the result to be in error.

5.5. Replacement of Participants

Participants may be replaced for any of the following reasons:

- In Phase 1, any participant who takes \leq 75% of the planned itacitinib doses up to the Week 12 visit for any reason.
- Participants who do not meet the eligibility requirements of the study.

6. STUDY TREATMENT

6.1. Study Treatment Administered

Information regarding study drug and administration is provided in [Table 8](#).

Once eligibility is confirmed, participants enrolling into Phase 1 will be randomized to an assigned dose level (see [Table 9](#)), will begin the treatment period on Day 1, and will continue on study treatment until discontinuation criteria are met.

Participants enrolling into Phase 2, upon confirmation of eligibility, will begin treatment at the RP2D determined in Phase 1.

Table 8: Study Treatment Information

Study treatment name:	Itacitinib	
Dosage formulation:	Sustained release tablet	
Unit dose strength:	100 mg	
Route of administration:	Oral	
Administration instructions:	
During Phase 1, participants will be randomized to 1 of 3 dose levels, as outlined in Table 9. Itacitinib administration will continue daily at the assigned dose until treatment discontinuation.
 
Phase 2 participants will be administered itacitinib at the RP2D, which will be selected based on the criteria outlined in Section 6.1.1.
 
Itacitinib may be taken without regard to food except on PK days.
 
Missed doses must be taken within 8 hours after the scheduled time of administration; however, if this window is not met, the missed dose will be documented as not taken and the next scheduled dose will be taken as scheduled.
	
Packaging and labeling:	
Itacitinib will be provided in 35-count bottles.
 
Investigational product labels will be in the local language and will be labeled as required per country requirement.
	
Storage:	Ambient 15°C-30°C (59°F-86°F)	

Table 9: Itacitinib Dose Levels

Itacitinib Dose Level	Starting Dose		First Dose Level Reduction		Second Dose Level Reduction	
	A: No CYP3A	B: With CYP3A	A: No CYP3A	B: With CYP3A	A: No CYP3A	B: With CYP3A
Dose Level 1	300 mg BID	200 mg BID	200 mg BID	100 mg BID	100 mg BID	100 mg QD
Dose Level 2	400 mg QD	300 mg QD	300 mg QD	200 mg QD	200 mg QD	100 mg QD
Dose Level 3	600 mg QD	400 mg QD	400 mg QD	300 mg QD	300 mg QD	200 mg QD

The assigned dose level (Dose Level 1, 2, or 3) will determine the dose and schedule of itacitinib to be administered as the starting dose as well as any subsequent reductions in dose that may occur due to toxicity. The dose administered will also be determined based on whether the participant is taking a concomitant strong CYP3A inhibitor (eg, voriconazole, itraconazole, posaconazole, ketoconazole; see [Appendix C](#)). **Participants who are not taking concomitant strong CYP3A inhibitor will be administered the dose specified in Column A of Table 9. Participants who are taking concomitant strong CYP3A inhibitor will be administered the dose specified in Column B of Table 9.** If a participant begins taking or discontinues a strong CYP3A inhibitor during treatment, the dose should be adjusted accordingly per [Table 9](#) (eg, if the participant begins taking a strong CYP3A inhibitor, he/she should be switched to the dose specified in Column B). At the time of either addition or discontinuation of a strong CYP3A inhibitor, close monitoring of CNI levels should be undertaken to ensure safety of the study participant.

Participants enrolled before Protocol Amendment 2 who were randomized to receive the 200 mg QD dose and who are ongoing at the time of amendment approval may increase their itacitinib dose to Dose Level 2 using the same parameters outlined in [Table 9](#), with approval from the sponsor. Participants must have tolerated the 200 mg QD dose and have not experienced any AEs \geq Grade 3 that are considered related to itacitinib. Additionally, the participant must agree to weekly clinic visits for a targeted physical examination and hematology/complete blood count assessment for the first 2 weeks after the dose increase.

Participants may have dose reductions or modifications during the course of treatment based on AEs, clinical evaluation, changes to concomitant medications, and laboratory assessments. Dose modifications of itacitinib for toxicity should follow the algorithm outlined for each dose level in [Table 9](#). See Section [6.2.1](#) for criteria and guidelines related to itacitinib dose modifications due to AEs and Section [6.3](#) for guidelines related to itacitinib dose modifications due to select concomitant medications.

Participants are permitted to remain on itacitinib treatment until withdrawal from study treatment is considered necessary as per Section [7.1.1](#).

6.1.1. Determination of Recommended Phase 2 Dose

After the final participant enrolled into the Phase 1 portion completes the Week 12 visit, a study steering committee comprised of the coordinating PI and Incyte personnel representing clinical development, pharmacovigilance, and statistics will review the cumulative Phase 1 data and provide a recommendation for the Phase 2 dose level. Additional details regarding the composition of the steering committee and the process by which the committee will review data and make recommendations will be documented in the steering committee charter.

The RP2D will be selected on the basis of AE, laboratory, PK, and PD observations through the Week 12 visit. One of 3 doses (Dose Level 1, Dose Level 2, or Dose Level 3) will be chosen to take forward into the Phase 2 portion of the study. Additionally, before opening enrollment into Phase 2, an efficacy analysis of FEV₁ response will be performed for each dose level to further inform RP2D selection, as described in Section [4.1](#). Phase 1 participants who are ongoing at the time of RP2D selection will remain on their initial dose level for the duration of the treatment period.

6.2. Dose Modifications

6.2.1. Criteria and Procedures for Dose Interruptions of Study Drug

Safety concerns should be discussed with the sponsor immediately upon occurrence or awareness to determine if the participant should continue or discontinue study treatment.

Treatment with itacitinib may be delayed up to 14 days to allow for resolution of toxicity. After interruption, participants should be evaluated on a weekly basis until resolution/improvement of the AE. Participants may resume treatment if no medical condition or other circumstance exists that, in the opinion of the investigator, would make the participant unsuitable for further participation in the study. The investigator should contact the medical monitor to discuss the case of any participant whose treatment has been delayed for more than 14 days before restarting treatment.

Because participants may enter the study with extensive comorbidities, dose reduction recommendations in [Table 10](#) are provided as guidelines. Each participant may undergo up to 2 dose reductions for toxicity. Individual decisions regarding dose modifications should be made using clinical judgment and an individual benefit/risk assessment taking into account relatedness of the AE to the study drug and the participant's underlying condition. Adverse events that have a clear alternative explanation, or transient (≤ 72 hours) abnormal laboratory values without associated clinically significant signs or symptoms, may be exempt from dose modification rules. The sponsor's medical monitor may be consulted for advice.

Table 10: Guidelines and Procedures for Interruption of Study Drug

ADVERSE EVENT	ACTION TAKEN
Chemistry	

• AST and/or ALT is $> 3.0 \times \text{ULN}$	
Step 1: Interrupt itacitinib administration up to 14 days until the toxicity has resolved to \leq Grade 1. Exceptions require sponsor approval.
 
Step 2: Restart itacitinib at previous dose. If assessed as related to itacitinib, restart at reduced dose level and monitor as clinically indicated.


• AST and/or ALT is $> 5.0 \times \text{ULN}$• ALT or AST is $> 3.0 \times \text{ULN}$ and total bilirubin is $> 2.0 \times \text{ULN}$ or INR is > 1.5 on repeat testing• AST and/or ALT is $> 3.0 \times \text{ULN}$ with the appearance of fatigue, nausea, vomiting, right upper quadrant pain or tenderness, fever, rash, and/or eosinophilia	Permanently discontinue itacitinib administration with close observation. Evaluation for other underlying causes should be sought.

Table 10: Guidelines and Procedures for Interruption of Study Drug (Continued)

ADVERSE EVENT	ACTION TAKEN
Hematology	
• Platelet count is 25 to $< 50 \times 10^9/\text{L}$	
Step 1: Interrupt itacitinib administration until the platelet count has resolved to $\geq 100 \times 10^9/\text{L}$.
 
Step 2: Restart at 1 dose level reduction.
 
Second occurrence: Repeat Steps 1 and 2; consult medical monitor before restarting itacitinib.
 
Third occurrence: Discontinue treatment.

• ANC is 0.5 to $< 1.0 \times 10^9/\text{L}$	
Step 1: Interrupt itacitinib administration up to 14 days until ANC has resolved to $\geq 1.0 \times 10^9/\text{L}$.
 
Step 2: Restart itacitinib at same dose, and monitor as clinically indicated.
 
Second occurrence: Restart at 1 dose level reduction.

• Platelet count is $< 25 \times 10^9/\text{L}$ or ANC $< 0.5 \times 10^9/\text{L}$	Interrupt itacitinib administration until the platelet count has resolved to $\geq 100 \times 10^9/\text{L}$. May resume treatment at 1 dose level lower after approval from medical monitor.
Other toxicities	
• Any Grade 1 or Grade 2 toxicity	Continue itacitinib administration, and treat the toxicity; monitor as clinically indicated.
• Any Grade 3 toxicity, if clinically significant and not manageable by supportive care.	
Step 1: Interrupt up to 14 days until toxicity resolves to \leq Grade 1.
 
Step 2: Restart at same dose; if assessed as related to itacitinib, restart at next lower dose and monitor as clinically indicated.

• Any Grade 4 toxicity	Discontinue itacitinib administration, and follow-up per Protocol.

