2.3. Benefit/Risk Assessment

The potential benefit for itacitinib in post-lung transplant BOS patients is derived from the biologic similarity to cGVHD, with each entity sharing common features such as increased proinflammatory cytokines, presence of CD4, CD8, and Th17 cell infiltrate, as well as subsequent recruitment of B cell, NK cell, and APCs. Preclinical models and small clinical studies have demonstrated significant activity when JAK inhibitors are used in cGVHD, including improvement and stabilization in FEV₁ in patients with lung cGVHD, suggesting that JAK inhibitors may also have potential utility in treating post-lung transplant BOS.

Risks to study participants may be minimized by compliance with the eligibility criteria and study procedures as well as close clinical monitoring and adherence to dose modification guidelines for toxicity. Additionally, the safety profile of the 3 doses to be evaluated has been established in prior studies. Risks related to myelosuppression and bleeding should be further managed in accordance to standard institutional practices for administration of hematopoietic growth factors and transfusion support. Risks related to infections should be managed through continued prophylaxis and prompt identification and treatment.

In September 2021, analysis of the data from the Phase 1 portion of the study revealed evidence of clinical benefit in a subset of participants with a manageable safety profile. The sponsor decided not to proceed to Phase 2 of the study for reasons unrelated to the benefit/risk of itacitinib in the study population. The sponsor will continue to consider the benefit/risk favorable for participants who are continuing on itacitinib as of Protocol Amendment 5.

There may be unforeseen and potentially serious risks with itacitinib. More detailed information about the known and expected benefits and risks and reasonably expected AEs of itacitinib may be found in the [IB](#).

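### Table 10 gives a platelet value, and no neutrophil value, for restarting itacitinib after ANC < 0.5 × 10⁹/L

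*Protocol*

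**What the plan says.** The hematology part of Table 10 (Protocol Section 6.2.1) has three rows. The first covers platelets of 25 to < 50 × 10⁹/L and holds drug until platelets reach 100. The second covers ANC of 0.5 to < 1.0 × 10⁹/L and holds drug for up to 14 days until ANC reaches 1.0. The third covers platelets < 25 or ANC < 0.5, either being sufficient, and holds drug "until the platelet count has resolved to $\geq 100 \times 10^9/\text{L}$. May resume treatment at 1 dose level lower after approval from medical monitor".

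The text above the table is general. It states "Treatment with itacitinib may be delayed up to 14 days to allow for resolution of toxicity" and that, after an interruption, "participants should be evaluated on a weekly basis until resolution/improvement of the AE". It leaves resumption to the investigator's opinion of suitability, asks for medical monitor contact when a delay exceeds 14 days, and describes the table's recommendations as guidelines. It gives no ANC value.

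**The concern.** Each row of a dose-interruption table should tie restart to recovery of the count that caused the stop. The third row does this for platelets but not for neutrophils. The protocol therefore fixes a neutrophil recovery value for the less severe neutropenia and none for the more severe.

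The participants are immunosuppressed lung transplant recipients. Protocol Section 2.3 names myelosuppression and infection as risks to be managed, and the Amendment 4 summary in Appendix E reports 5 participants with CMV viremia or reactivation needing antiviral treatment. SAP Section 9.2.3 lists neutropenia as a clinically notable category, and SAP Appendix B includes febrile neutropenia and neutropenic sepsis in it. Neutrophil recovery is the value one would want settled before re-exposure. As written, the investigator and medical monitor must supply it case by case.

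**Working it through.** There is no sample size, power or event count to reproduce. The check sets triggers against recovery values and then applies the written rule to each platelet range. All counts are × 10⁹/L.

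**Step 1. Trigger against recovery value (Table 10, hematology), with the combined row separated into its two triggers.**

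| Trigger | Laboratory value for restart | Same count as trigger? | Dose at restart | Medical monitor |
|---|---|---|---|---|
| Platelets 25 to < 50 | Platelets ≥ 100 | Yes | One level lower | Consulted before restart at second occurrence |
| ANC 0.5 to < 1.0 | ANC ≥ 1.0 | Yes | Same; one level lower at second occurrence | Not named in the row |
| Platelets < 25 | Platelets ≥ 100 | Yes | One level lower | Approval needed |
| ANC < 0.5 | Platelets ≥ 100 | **No** | One level lower | Approval needed |

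Only the last trigger lacks a matching recovery value.

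**Step 2. Participant with ANC < 0.5, by platelet count.** The written restart condition is platelets ≥ 100. Platelets alone cause an interruption only below 50.

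| Platelets at interruption | Restart condition met at once? | Consequence |
|---|---|---|
| ≥ 100 (e.g. 150, 120, 100) | Yes | Nothing in the laboratory condition waits for ANC to recover |
| 50 to < 100 (e.g. 99, 60, 50) | No | Hold lasts until platelets reach 100, even after ANC recovers; no row interrupts for these platelet counts |
| 25 to < 50 | No | The platelet row applies in its own right, with the same value of 100; still no ANC value |
| < 25 | No | Both triggers of the combined row are met; still no ANC value |

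The rule can therefore err in either direction. The first case is plausible: exclusion criterion 14 (Section 5.2, Table 7) removes candidates with platelets < 120 at screening, although that floor does not apply on treatment.

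**Step 3. Does other text supply the value?** The general wording of Section 6.2.1 does not. The instruction to discontinue for any Grade 4 toxicity sits under other toxicities, whereas the combined hematology row expressly allows resumption, so it does not clearly govern here.

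**Step 4. Frequency.** The only related counts in the documents are Grade 3/4 treatment-related neutropenia in acute GVHD (Section 2.2, Figure 5): 0 of 14 at 200 mg and 1 of 15 at 300 mg QD. That is a different disease, at doses below the full starting doses here (400 mg QD, 600 mg QD and 300 mg BID in Table 9). No rate for this trial can be derived from them.

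**The case against.** The strongest reply is that the table, read as a whole, implies the missing value. While ANC is < 0.5, the row's own trigger is still met. Between 0.5 and < 1.0, the participant falls under the row above, which interrupts until ANC ≥ 1.0. Restarting at any ANC < 1.0 would put the participant straight into a state that calls for interruption. A careful reader would reach this floor, but only by inference: nothing says that triggers are re-checked at restart. The inference also leaves in place the unrelated platelet condition for participants with platelets of 50 to < 100.

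Safeguards also stand between the written rule and harm: "May resume treatment at 1 dose level lower after approval from medical monitor", the reference to resolution of toxicity, investigator judgment and the table's status as guidelines. These make an unsafe automatic restart unlikely. They settle who approves and at what dose, not what neutrophil count is needed. A guideline still has to point to the right count.

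A prolonged hold is the cautious direction, and no harm from it is shown, so that half of the point is the weaker one. It is also fair to call this a drafting omission rather than a contradiction between two passages. Whatever the label, the stated condition is the wrong one for a participant who enters on ANC alone.

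Finally, Phase 2 was cancelled and enrollment is closed. That limits the practical reach of the point.

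**Conclusion.** The concern holds. For ANC < 0.5 × 10⁹/L as the only trigger, the written laboratory condition is either already satisfied (platelets ≥ 100) or unrelated to the reason for stopping (platelets below 100). This is an error in a stated safety rule. Existing safeguards partly offset it, so it should be corrected but is not critical.

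Its size cannot be put as a rate. No effect on an endpoint, or on the SAP's summaries of interruptions, is claimed.

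The practical value depends on whether anyone is still being treated. Protocol Section 2.3 refers to "participants who are continuing on itacitinib as of Protocol Amendment 5", Section 4.2 keeps ongoing participants on treatment under the protocol after database lock, and Section 6.7 provides for drug after the study ends. The documents do not show whether any participant remains on drug. If none does, the correction has no effect in this study.

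**What to change.** Split the combined row by trigger:

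- **ANC < 0.5 × 10⁹/L:** interrupt until ANC ≥ 1.0 × 10⁹/L, the value in the adjacent row, or a stricter value set by the sponsor.
- **Platelets < 25 × 10⁹/L:** interrupt until platelets ≥ 100 × 10⁹/L.
- **Both:** require both recovery values.

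Keep the one-level dose reduction and medical monitor approval in every case.

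The cost is a one-row protocol clarification and a letter to sites. No new procedure is needed: neutrophils are already in the required hematology panel (Section 8.3.5, Table 11), and weekly evaluation during an interruption is already recommended, though not worded as mandatory. Section 11.1 adds an administrative step, because protocol changes go through the sponsor and the IRB/IEC before they are implemented, other than to remove an immediate hazard. The sponsor should first confirm whether any participant is still receiving itacitinib.
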